An adverse event (AE) is any untoward medical occurrence associated with the use of a drug in humans whether or not considered drug related. FDA, Office of Human Research Protection (OHRP), and NeuroNEXT CIRB requirements for reporting AEs will be followed. Subjects who receive investigational treatment will be monitored for AEs from the time they sign consent until 7 days for AEs and 30 days for SAEs following permanent discontinuation of study drug. At that point, all ongoing AEs will be followed to resolution, or until Day 90, but no new AEs will be recorded. The IMM/DSMB will review cumulative AEs; the frequency of this review will be determined by the IMM/DSMB in conjunction with the Protocol PI.

Each Clinical Study Site Principal Investigator (CSS PI) and research team (co-Investigators, research nurse, clinical trial coordinator) are responsible for identifying and reporting AEs. The CSS PI is responsible for determining the relationship of the event to the study drug/study procedures. Aggregate reports blinded by treatment group, detailed by severity, attribution (expected or unexpected), and relationship to the study drug/study procedures, will be available from the DCC for review by the IMM. A separate report detailing protocol compliance will also be available monthly from the DCC for review by the Protocol PI, who will provide feedback to individual sites as needed. The Protocol Steering Committee (PSC) will advise the Protocol PI as to whether the protocol or informed consent document requires revision based on these reports.

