9.4 Adverse Experience Reporting

The adverse event (AE) definitions and reporting procedures provided in this protocol comply with all applicable United States Food and Drug Administration (FDA) regulations and International Conference on Harmonization (ICH) guidelines. The Site Investigator will carefully monitor each subject throughout the study for possible adverse events. All AEs will be documented on CRFs designed specifically for this purpose. It is important to report all AEs, especially those that result in permanent discontinuation of the investigational product being studied, whether serious or non-serious.

AEs should be collected and reported on subjects who receive investigational treatment from signing of the ICF through study Day 7, and should be followed until resolution or a new baseline is established, but no longer than study Day 90. Any AEs that occur prior to informed consent should be included in the subject's medical history. SAEs will be collected and reported on subjects who receive investigational treatment from signing of the ICF through study Day 30, and should be followed until resolution (or resolution with sequelae), but no longer than study Day 90.

Each clinical study site's Principal Investigator and research team are responsible for identifying adverse events and reporting them through the DCC Online Adverse Event Reporting System. Investigators are also responsible for complying with NeuroNEXT CIRB's reporting requirements for all safety reports. Copies of each report and documentation of IRB notification and receipt will be kept in the Investigator's study file.

Headache has been identified as an AE that we would like to further characterize. Therefore, all headaches that start after signing of the ICF should be documented as AEs, and Investigators should also complete the Headache Record CRF. A new AE form and new Headache Record should be completed for each new headache during the first seven days. Headaches that start prior to signing of the ICF and do not worsen should be reported only on the Medical History CRF and the Headache Record CRF should not be completed. If however, a headache begins prior to consent and later worsens it should be reported as an AE and the Headache Record CRF should be completed.

On-line Adverse Event Reporting System

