Each subject will be followed for 90 days in this study. Subjects will be considered for the study after beginning tPA administration, mechanical thrombectomy, or both for moderate to severe acute ischemic stroke. Eligible subjects will receive 3K3A-APC or placebo every 12 hours for up to 5 doses (approximately 3 days), or until discharge from this hospital – whichever occurs first. Subjects will be monitored for safety evaluations through Day 7. Subjects are expected to be seen for assessments on Days 7, 14, 30, and 90. MRI scans, including SWI sequences, will be obtained at Day 7 (or discharge), Day 30, and Day 90.

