Subjects who sign consent and receive investigational treatment will be monitored for AEs from the time they sign consent through Day 7. Any AEs that occur prior to informed consent should be included in the subject's medical history. This study will utilize the CTCAE version 4.03 coding system for adverse event recording. AEs reported using CTCAE will be recoded into MedDRA terms by the DCC, with the exception that events of "Intracranial Hemorrhage", "Cerebral Hematoma", or "SICH" are coded as "Cerebral Hemorrhage" and events of "Infarct Extending" are coded as "Cerebrovascular Accident" (per request of PPI).

At each visit (including telephone interviews), the subject will be asked "Have you had any problems or symptoms since your last visit?" in order to determine the occurrence of AEs. If the subject reports an AE, the Investigator will determine:

- Type of event
- Date on onset and resolution (duration)
- Severity (mild, moderate, severe, life-threatening, results in death)
- Seriousness (does the AE meet the definition of an SAE)
- Causality, relation to investigational product and disease
- Action taken regarding investigational product
- Outcome

All clinical AEs are recorded in the AE data entry template in the subject's study binder. The site should fill out the AE data entry template and enter the information into the Online Adverse Event Reporting System (AERS) within 5 working days / 7 calendar days of the site learning of a new AE or receiving an update on an existing AE. Entries in the AE data entry template will include the following:

- Name and severity of the AE
- Date of onset
- Date of resolution
- Relationship to study drug
- Action taken

- Primary outcome of event

The severity of all AEs will be graded according to CTCAE, version 4.03. Any AE not listed in the CTCAE will be graded as follows:

- Grade 1 – Mild: Transient or mild discomfort; No limitation in activity; No medical intervention/therapy required
- Grade 2 – Moderate: Mild to moderate limitation in activity; Some assistance may be needed; No or minimal medical intervention/therapy required
- Grade 3 – Severe: Marked limitation in activity, some assistance usually required; Medical intervention/therapy required; Hospitalizations possible
- Grade 4 – Potentially Life-Threatening: Extreme limitation in activity; Significant assistance required; Significant medical intervention/therapy required; Hospitalization or hospice care probable

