Serious adverse events (SAEs) will be collected and reported on subjects who receive investigational treatment from signing of ICF through study Day 30. All SAEs must be reported within 24 hours of the site being notified of the event. All SAEs should be followed until resolution (or resolution with sequelae), but no longer than Day 90.

The Protocol PI will appoint an Independent Medical Monitor (IMM). Upon entry of an SAE by a clinical site, the NeuroNEXT Online Adverse Event Reporting System (AERS) will immediately notify the IMM. The IMM will review the SAE report to assess seriousness, expectedness and relatedness to study treatment, and may request further information if necessary. An unexpected SAE is any SAE for which the specificity or severity is not consistent with the current Investigators Brochure or package insert or described in the protocol. An unexpected, suspected adverse drug reaction is any unexpected SAE that, in the opinion of the IMM is at least possibly related to study treatment. Such SAEs (unexpected and at least possibly treatment-related) require expedited reporting to the FDA. The DCC will prepare a MedWatch safety report for submission to the FDA. If warranted, the IMM will notify the DSMB chair.

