10.8 Safety Analyses

In addition to the determination of an MTD, additional safety assessments will involve a comparison of treatment-related AEs and SAEs across all 3K3A-APC treated subjects (regardless of dose) versus placebo. First, the percentage of subjects who experience any treatment-related AE or SAE in each group will be compared using a Fisher's exact test. If the null hypothesis is rejected, with a greater frequency observed in the 3K3A-APC group, we will conclude that 3K3A-APC was associated with a significantly greater frequency of treatment-related AEs. If the hypothesis is not rejected, we will conclude that the study does not provide sufficient evidence to conclude that 3K3A-APC was associated with a significantly greater frequency of treatment-related AEs. In addition to an overall comparison, this hypothesis will be repeated for the percentage of subjects having at least one treatment-related AE within each MedDRA system organ class (SOC). If there are significant differences between groups within any specific SOC, then additional tests will compare differences across groups for specific MedDRA preferred terms in order to further explore the cause of observed differences.

In addition to the comparison of percentages in the manner described above, the rates of treatment-related AEs in each group will be compared using the following Poisson regression model:

$$\log\left(\frac{Y_i}{T_i}\right) = \beta_0 + \beta_1 x_{1i} + \epsilon_i$$

where

- Y_i represents the number of treatment related SAEs experienced by the i^{th} subject.
- T_i represents the number of days between the date of randomization and the date of last follow-up for the i^{th} subject.
- $x_i = 1$ if i^{th} subject was randomized to one of the 3K3A-APC dose groups, and 0 if the subject was randomized to placebo group
- ϵ_i is random error for the i^{th} subject

To determine if the rate of treatment related SAEs differ across treatment group we will test the following hypothesis:

$$H_0: \beta_1 = 0 \text{ vs. } H_A: \beta_1 \neq 0$$

If the null hypothesis is rejected, the direction of β_1 will indicate the direction of the observed effect. Values of $\beta_1 > 0$ indicate an increased rate of treatment-related AEs associated with the 3K3A-APC group, while values of $\beta_1 < 0$ indicate a decreased rate of treatment-related AEs associated with the 3K3A-APC group.

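### Minor: the SAP 10.8 Poisson model counts exposure to last follow-up, past the Day 7 AE and Day 30 SAE cut-offs, so its rate ratio is biased when early exits differ by arm

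*SAP*

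**What the plan says.** SAP 10.8 introduces the Poisson model as a supplement: "In addition to the comparison of percentages in the manner described above, the rates of treatment-related AEs in each group will be compared". The exposure T_i "represents the number of days between the date of randomization and the date of last follow-up". Nothing in 10.8 defines last follow-up or caps T_i.

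Other sections set the time frames:

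- SAP 1: "Each subject will be followed for 90 days in this study".
- SAP 10.1: treated subjects "will be monitored for AEs from the time they sign consent through Day 7". Protocol 9.4 agrees: "from signing of the ICF through study Day 7".
- SAP 10.2: SAEs are collected "from signing of ICF through study Day 30".
- Protocol 8.4, on what happens once the window closes: "all ongoing AEs will be followed to resolution, or until Day 90, but no new AEs will be recorded". This section runs the windows differently, however: "until 7 days for AEs and 30 days for SAEs following permanent discontinuation of study drug".

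The model is announced for treatment-related AEs, but SAP 10.8 then defines Y_i as a count of treatment-related SAEs. The end of 10.8 says that SAEs are handled the same way, so an AE model and an SAE model are evidently both meant. It extends the approach to treatment-emergent events, neuroworsening, DLTs and deaths, and repeats everything for each dose against placebo, without saying which T_i applies.

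**The concern.** An exposure offset should count only time in which the event could have been recorded. With 90-day follow-up, last follow-up is naturally read as about Day 90 for a completer. A subject who completes the study and one who dies on Day 10 have both passed through the whole 7-day AE window, yet their T_i are about 90 and about 10.

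The arm that loses more subjects early therefore loses denominator but almost no time at risk, and its event rate is pushed up. If the drug reduced early death, its AE rate would look falsely low. If it increased early death, its AE rate would look falsely high. Either is unwelcome in a safety comparison where, on rejection, the SAP reads the direction of effect from the sign of the coefficient.

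**Working it through.** The documents give no rate, power or sample size for this model, so there is no planned figure to reproduce.

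**Formula.** With a log(T) offset and one treatment indicator, the fitted rate ratio is

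exp(β1) = (ΣY₁/ΣT₁) / (ΣY₀/ΣT₀).

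A fitted GLM on simulated data agreed with this expression (0.89897 both ways). Let W be the collection window (7 or 30 days) and w = min(T, W). If both arms have the same event rate while at risk, the ratio that should be 1 becomes

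bias = (mean w₁ / mean w₀) × (mean T₀ / mean T₁).

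If exits are alike in frequency and timing, this equals 1.

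**Inputs.** From the documents: 90-day follow-up, windows of 7 and 30 days, 22 × 3 = 66 on drug, and about 115 − 66 = 49 on placebo. Assumed, because the documents give no mortality for this trial: 10% on drug and 20% on placebo, deaths uniform over Days 2-30 (alternatively 2-90), everyone else followed to Day 90.

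**Deaths over Days 2-30** (mean death day 16):

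- Mean T: 0.9×90 + 0.1×16 = 82.6 on drug; 0.8×90 + 0.2×16 = 75.2 on placebo.
- Mean AE time at risk of those who die: (22.5 + 7×23)/28 = 6.554 days. Mean w: 0.9×7 + 0.1×6.554 = 6.955; 0.8×7 + 0.2×6.554 = 6.911.
- AE bias: (6.955/6.911) × (75.2/82.6) = 0.916.
- SAE: mean w is 0.9×30 + 0.1×16 = 28.6 and 0.8×30 + 0.2×16 = 27.2. Bias: (28.6/27.2) × (75.2/82.6) = 0.957.

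**Other patterns, same formula:**

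| Mortality drug / placebo | Death days | AE ratio | SAE ratio |
|---|---|---|---|
| 10% / 20% | 2-90 | 0.951 | 0.963 |
| 20% / 10% | 2-30 | 1.091 | – |
| 20% / 10% | 2-90 | 1.052 | – |
| 15% / 15% | same timing | 1.000 | 1.000 |
| 15% / 15% | 2-90 drug, 2-30 placebo | 0.952 | – |
| 21% / 22% | 2-30 | 0.991 | 0.995 |
| 18.4% / 15.5% | 2-30 | 1.026 | 1.013 |
| 9.2% / 12.4% | 2-30 | 0.974 | 0.987 |

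The last three rows borrow the smaller mortality gaps in Protocol Table 1.

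**Test size.** 20,000 simulated trials per setting, 66 vs 49, no true effect, 10% vs 20% mortality, two-sided Wald test on the log AE rate ratio:

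| AEs per subject | Deaths Days 2-30: SAP T | Days 2-30: window T | Deaths Days 2-90: SAP T | Days 2-90: window T |
|---|---|---|---|---|
| 0.2 | 5.0% | 3.8% | 4.2% | 3.6% |
| 0.3 | 5.8% | 4.2% | 4.8% | 4.3% |
| 0.5 | 6.8% | 4.8% | 5.4% | 4.6% |
| 1 | 9.1% | 4.9% | 5.9% | 4.6% |
| 2 | 13.1% | 4.9% | 7.7% | 4.7% |

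At 0.3 AEs per subject with deaths over Days 2-30, the errors fall mainly on one side: 4.7% falsely lower on drug and 1.1% falsely higher, against 2.2% and 2.0% with window time. For SAEs at 0.3-0.5 per subject the size is 4.7-5.3%, against 4.5-4.7%. With 15% mortality and equal timing in both arms it is 4.5-5.2% at 0.3-0.5 AEs. Single-dose comparisons are no worse: at 0.3-1 AEs per subject, 30 vs 49 gives 4.5-7.1% and 12 vs 49 gives 2.4-5.6%.

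A separate simulation (4,000 runs per setting, exits uniform over Days 1-90, 0.05 AEs or 0.01 SAEs per day at risk, exits equal at 15% or differing by as much as 9% vs 22%) gave sizes of 4.0-5.6% with the SAP exposure and 3.9-5.0% with window exposure. With exits at 15% in both arms, chance imbalance alone moved the ratio by about ±8% (AEs) or ±6% (SAEs).

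**The case against.** The strongest reply is that the illustration is severe. Gaps near 10% vs 20% do appear in Protocol Table 1 (10.4% vs 19.0%, 9% vs 20%), but there they compare thrombectomy with a tPA-only control. Here both arms receive recanalization treatment, so those contrasts do not carry over. The other three trials in that table show gaps of 1 to 3 points, and those give ratios of only 0.97 to 1.03. This stands: 10% vs 20% is a stress case, not a forecast.

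Second, the larger test sizes need 1 or 2 events per subject. The model is introduced for treatment-related events, where such counts are unlikely. Counts near 2 are plausible only for all treatment-emergent AEs, to which 10.8 does extend the method. If Y_i is read literally as SAEs, inflation is negligible. This also stands, although the end of 10.8 favours the reading that AEs and SAEs are each modelled.

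Third, dosed subjects are to be followed to the end of the study (Protocol 4.4.4, SAP 4) and undosed subjects are outside the safety population (SAP 6.4), so unequal exit would come mainly from deaths. That narrows the route for bias but leaves its principal source.

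Last, Day 90 is an inference. If last follow-up meant the end of event collection, the problem would vanish. But no section says so, SAP 1 points to Day 90, and the text would still need that definition.

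**Conclusion.** The concern holds and is minor. As written, T_i is the wrong denominator for AEs and SAEs, and no other section corrects it. The rate ratio is unbiased when early exits match by arm in frequency and timing. Under the assumed 10% vs 20% mortality, the null AE ratio becomes 0.92 (0.95 with later deaths) and the SAE ratio 0.96; under gaps of 1 to 3 points, both stay within about 3% of 1. Test size at the AE counts plausible for treatment-related events moves by at most about 2 points. These figures rest on assumed mortality, timing and event counts, and on reading last follow-up as about Day 90.

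The reach is limited. The model supplements Fisher's exact test, and neither that test nor the CRM or MTD uses T_i. The SAP asks for no absolute per-day rate. If one were reported, it would be too low by about 90/7 = 12.9-fold for AEs (90/10 = 9-fold if the window runs 7 days from a last dose on Day 3) and 90/30 = 3-fold for SAEs, even with equal exits.

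**What to change.** In SAP 10.8, define T_i by event type as days from randomization to the earliest of death, withdrawal and the end of that event's collection window: Day 7 for AEs and Day 30 for SAEs, as SAP 10.1 and 10.2 now stand. Keep last follow-up only for deaths, and only if deaths are captured to Day 90.

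For DLTs and neuroworsening, do not end T_i at 48 hours after the last dose. A DLT itself stops dosing (Protocol 3.1.1, 4.3.2), so exposure would depend on the outcome. With five doses 12 hours apart, that window is 4 days without a DLT but 2 days after a DLT at dose 1. A true ratio of 2.0 (10% vs 5%) would read 2×(0.95×4 + 0.05×2)/(0.90×4 + 0.10×2) = 2.05 if all DLTs followed dose 1. Use the Fisher comparison of proportions already planned, or a fixed window that does not depend on the event.

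Write Y_i as AEs in the AE model and as SAEs in the SAE model. Reconcile Protocol 8.4, which counts the windows from drug discontinuation, with Protocol 9.4 and SAP 10.1-10.2, which use study day. Either version ends well before Day 90, so the need for a cap does not depend on the outcome.

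The cost is SAP wording and a few lines of code, with no new data.
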